2.1. Overall Study Design

This is a multicentre, Phase 1/2, open-label clinical trial of the VTP-850 prime-boost immunotherapeutic in men with biochemical recurrence after definitive local therapy for prostate cancer.

Participants in all cohorts will receive the ChAdOx1-PCAQ component on Day 1 (prime) and the MVA-PCAQ component on Days 29 and 57 (boosts; Intervention Period). Participants will be followed until the Month 6 Visit or start of new therapy such as ADT or until development of unequivocal metastatic prostate cancer (Short-term Follow-up Period). Participants who have a PSA response will be followed for an additional 18 months, up to 24 months from first dose, or until start of new therapy such as ADT or development of unequivocal metastatic prostate cancer (Long-term Follow-up Period). In the event that a participant experiences a confirmed PSA response but subsequently experiences PSA progression more than 2 months after their final dose of VTP-850, an additional dose of MVA-PCAQ may be offered to the participant if the investigator believes it may be in the participant's best interest, after discussion with the medical monitor and agreement of the SMC.

Phase 1 will determine the recommended Phase 2 regimen (RP2R; the dose level of both ChAdOx1-PCAQ and MVA-PCAQ and the route of administration of MVA-PCAQ) that will be used in Phase 2 and will follow a 3+3 design.

The first 3 participants will be enrolled in Cohort 1. Enrolment of the first 3 participants in each cohort will be staggered by at least 9 days. The medical monitor will review the safety data for the previous participant, at least 7 days after the prime dose and after the first booster dose of VTP-850, before the corresponding dose is administered to the next participant. The safety review will include data from at least 7 days after each ChAdOx-PCAQ prime dose; at least 7 days after the first booster MVA-PCAQ dose if administered intramuscularly (IM); and at least 14 days after the first booster dose of MVA-PCAQ if administered intravenously (IV). If 1 or more of the 3 participants has a dose limiting toxicity (DLT), 3 additional participants may be enrolled into Cohort 1. If there is no DLT after the first dose of VTP-850 in the first 3 participants, 3 participants will be enrolled into each of Cohorts 2 and 3 concurrently, with the first participants in Cohorts 2 and 3 staggered by at least 9 days to allow for medical review. If DLT is not seen in more than 1 participant in Cohort 2 after the first dose of VTP-850, then an additional 3 participants will be enrolled into Cohort 2. Safety data for the DLT period following each booster dose will be assessed by the medical monitor prior to the corresponding booster dose being administered to additional participants. If DLT is not seen after the first dose of VTP-850 in more than 1 participant in Cohort 3 then an additional 3 participants will be enrolled into Cohort 3. Safety data for the DLT period following each booster dose will be assessed by the medical monitor prior to the corresponding booster dose being administered to additional participants.

This SAP will cover the analyses for the Phase 1 part of the study. Phase 2 has not commenced and therefore any analyses related to or more applicable to the phase 2 part of the study are not covered in this SAP. A separate SAP will be written to cover the phase 2 part of the study in future.

2.2. Study Objectives

2.2.1. Primary Objective(s)

To evaluate the safety of VTP-850 prime-boost regimens, with the booster dose administered either IM or IV, and to establish an RP2R.

2.2.1.1. Endpoints for the Primary Objective(s)

- Number and proportion of participants with AEs, treatment-related AEs, \geq Grade 3 AEs, \geq Grade 3 treatment-related AEs, serious adverse events, and treatment-related serious adverse events
- Number and proportion of participants with clinically significant laboratory values
- Change from baseline for laboratory tests, electrocardiogram and vital sign measurements at each time point of collection

Full details for each endpoint are provided in Section 6.7.

2.2.2. Secondary Objective(s)

- To evaluate the PSA response rate to VTP-850
- To evaluate the durable PSA response rate to VTP-850

The following objectives are only applicable to the phase 2 of the study, and therefore will not be addressed in this phase 1 SAP:

- To evaluate the duration of PSA response to VTP-850 (for the subset of participants with PSA response)
- To assess the metastasis-free survival (MFS) and time to metastases (TTM) of the subset of participants with PSA response
- To assess the time to start of ADT for the participants with PSA response

2.2.2.1. Endpoints for the Secondary Objective(s)

The following are the relevant endpoints corresponding to the secondary objectives in the phase 1 part of this study:

- Percentage of participants with $\geq 50\%$ reduction in serum PSA compared to baseline at any time, based on two consecutive measurements at least 2 weeks apart
- Percentage of participants with confirmed PSA response compared to baseline without having PSA progression on or before Month 8

Full details for each endpoint are provided in Section 6.6.2.

2.2.3. Exploratory Objective(s)

- To characterise immunogenicity (including antigen-specific T-cell magnitude, phenotype and functionality associated with each regimen)

The following objectives are only applicable to the phase 2 of the study, and therefore will not be addressed in this phase 1 SAP:

- To explore association of PSA response with biomarkers
- To look for evidence of resolution of lesions on prostate-specific membrane antigen (PSMA) scan after administration of VTP-850 (if documented at baseline), and association of resolution of such lesions with PSA response in the subset of participants with baseline PSMA scan who have a PSA response on trial
- To assess the MFS and TTM of all participants

2.2.3.1. Endpoints for the Exploratory Objective(s)

The following are the relevant endpoints corresponding to the exploratory objectives in the phase 1 part of this study:

- CD4+ and CD8+ T-cell response to the VTP-850 antigens in the peripheral blood as measured by multi-parameter flow cytometry and enzyme linked immunospot assays (ELISpot)

Full details for each endpoint are provided in Section 6.6.4.

2.3. Sample Size and Power

A total of approximately 144 participants will be enrolled. Approximately 25 participants will be enrolled into the Phase 1 of the study. A sample size of approximately 125 participants will be eligible for inclusion in the Phase 2 efficacy evaluation. Full details of the sample size calculation are provided in the protocol Section 11.4.

2.4. Primary Efficacy Variable(s)

Not Applicable.

2.5. Secondary Efficacy Variable(s)

Prostate-specific antigen (PSA) is measured using blood samples for high-sensitivity serum PSA and is assessed at the central laboratory. Samples are collected at Screening, baseline (Day 1), Day 29, 57, 64, 91 and then in monthly intervals from Months 4 to 12 and then every 2 months to Month 24. Measurements from Months 7 to 24 are only made if a participant has a PSA response within the first 6 months and only until the start of new therapy such as ADT or development of unequivocal metastatic prostate cancer. Baseline PSA is defined using the

rules for baseline specified in Section 5.1.2. PSA response and progression are defined in Section 6.6.2. Missing values will not be imputed.

2.6. Exploratory Efficacy Variable(s)

2.6.1. Intracellular Cytokine Staining

Prostate cancer-specific CD4+ and CD8+ T cell subsets will be further defined by phenotypic markers of activation, differentiation, memory and functionality using multiparameter flow cytometry assays such as intracellular cytokine staining (ICS). Immunogenicity endpoints analyzed by Barinthus Bio's Immunology laboratory will be evaluated from PBMC samples at Days 1, 29, 36, 57, 64, 91 and Months 8 and 12. Participants who receive an optional third MVA dose or whose second MVA dose is delayed because of the study pause will have additional PBMC samples collected after this last MVA dose.

For the ICS data, the general class of endpoints is the background-subtracted (i.e., DMSO-subtracted) percentage of CD4+ or CD8+ T-cells that positively express at least one of four cytokines (as described in Table 2). For CD4+ cells, the four cytokines of interest are CD154, IFNg, TNFa, and IL-2. For CD8+, the four cytokines of interest are CD107a, IFNg, TNFa, and IL-2 (i.e., IFNg, TNFa, and IL-2 are common cytokines of interest for CD4+ and CD8+ cells).

Cytokine expression in CD4+ and CD8+ cells will be assessed for four stimulation antigens: PSA, PAP, 5T4, STEAP1. Hence, for each timepoint for a participant, the ICS data will include 4 records of interest, one for each of the 4 stimulation antigens¹.

Background-subtracted percentages of positive cytokine expression are calculated as follows:

1. For each sample's four stimulation antigens (i.e., PSA, PAP, 5T4, STEAP1), calculate the percentage of CD4+ or CD8+ cells with total positive cytokine expression (i.e. all combinations in Table 2) by dividing the cell count with positive expression by the respective total CD4+ or CD8+ count for the sample.
2. Likewise, calculate the background percentage of CD4+ or CD8+ cells with positive expression using the same method and the sample's DMSO record.
3. The background-subtracted percentage with positive cytokine expression is the subtraction of the background percentage expression calculated in Step 2 from the percentage calculated in Step 1. If the background expression is greater than the stimulation antigen's expression, the percentage with positive expression for the stimulation antigen should be set to 0.

¹ In addition to records for the 4 stimulation antigens of interest, the ICS data also include 3 additional stimulation records at each timepoint. CMV is an antigen-specific T cell response positive control, PMA is an assay positive control, and DMSO is the background/negative control. For analysis, the CMV and PMA stimulations can be ignored. The DMSO stimulation is used to determine the background-subtracted count of positively expressed CD4+ or CD8+ cells for each cytokine as noted above.

For example, calculation of the percentage of CD4+ cells with positive expression of all 4 CD4+ cytokines of interest (i.e., CD154, IFNg, TNFa, and IL-2) for the 5T4 antigen would be as follows using the hypothetical data below:

Participant ID	Timepoint	Stimulation	CD4 count	CD4/107+154+IFNg+IL2+TNFa+	CD4/107-154+IFNg+IL2+TNFa+
1	Day 29	DMSO	101599	3	16
1	Day 29	PSA	103404	0	5
1	Day 29	PAP	103093	0	1
1	Day 29	5T4	103111	461	6316
1	Day 29	STEAP1	106261	0	0
1	Day 29	CMV	108116	0	0
1	Day 29	PMA	91592	0	4

1. For 5T4, the count of CD4+ cells that positively express CD154, IFNg, TNFa, and IL-2 is:
461 (i.e., the CD4+ cells that also express CD107) +
6316 (i.e., the CD4+ cells expressing the 4 cytokines of interest without CD107) =
6777

The percentage of CD4+ cells expressing all 4 cytokines is therefore:
 $(6777/103111) \times 100 = 6.573\%$

2. For DMSO, the equivalent background count of cells expressing all 4 cytokines is 3 + 16 = 19.

Expressing this as a background percentage of expression is calculated as:
 $(19/101599) \times 100 = 0.019\%$

3. Hence, the background-subtracted percentage with positive expression of all 4 cytokines for the 5T4 antigen is $6.573 - 0.019 = 6.554\%$

For each T cell, 15 cytokine combinations (Table 1) per stimulation antigen will be calculated for summarization using the approach documented above. Note that the all-negative response categorization, where no cytokine is expressed, does not need to be calculated.

Table 1: ICS Cytokine Response Combinations

T Cell	Cytokines (%)	Cytokine combination naming
CD4+	CD4/CD107a+CD154+IFNg+IL2+TNFa+	IFNg+ / IL2+ / TNFa+ / CD154+
	CD4/CD107a-CD154+IFNg+IL2+TNFa+	
	CD4/CD107a+CD154-IFNg+IL2+TNFa+	IFNg+ / IL2+ / TNFa+ / CD154-
	CD4/CD107a-CD154-IFNg+IL2+TNFa+	
	CD4/CD107a+CD154+IFNg+IL2+TNFa-	IFNg+ / IL2+ / TNFa- / CD154+
	CD4/CD107a-CD154+IFNg+IL2+TNFa-	
	CD4/CD107a+CD154-IFNg+IL2+TNFa-	IFNg+ / IL2+ / TNFa- / CD154-
	CD4/CD107a-CD154-IFNg+IL2+TNFa-	
	CD4/CD107a+CD154+IFNg+IL2-TNFa+	IFNg+ / IL2- / TNFa+ / CD154+
	CD4/CD107a-CD154+IFNg+IL2-TNFa+	
	CD4/CD107a+CD154-IFNg+IL2-TNFa+	IFNg+ / IL2- / TNFa+ / CD154-
	CD4/CD107a-CD154-IFNg+IL2-TNFa+	
	CD4/CD107a+CD154+IFNg+IL2-TNFa-	IFNg+ / IL2- / TNFa- / CD154+
	CD4/CD107a-CD154+IFNg+IL2-TNFa-	
	CD4/CD107a+CD154-IFNg+IL2-TNFa-	IFNg+ / IL2- / TNFa- / CD154-
	CD4/CD107a-CD154-IFNg+IL2-TNFa-	
	CD4/CD107a+CD154+IFNg-IL2+TNFa+	IFNg- / IL2+ / TNFa+ / CD154+
	CD4/CD107a-CD154+IFNg-IL2+TNFa+	
	CD4/CD107a+CD154-IFNg-IL2+TNFa+	IFNg- / IL2+ / TNFa+ / CD154-
	CD4/CD107a-CD154-IFNg-IL2+TNFa+	
	CD4/CD107a+CD154+IFNg-IL2+TNFa-	IFNg- / IL2+ / TNFa- / CD154+
	CD4/CD107a-CD154+IFNg-IL2+TNFa-	
	CD4/CD107a+CD154-IFNg-IL2+TNFa-	IFNg- / IL2+ / TNFa- / CD154-
	CD4/CD107a-CD154-IFNg-IL2+TNFa-	
	CD4/CD107a+CD154+IFNg-IL2-TNFa+	IFNg- / IL2- / TNFa+ / CD154+
	CD4/CD107a-CD154+IFNg-IL2-TNFa+	
	CD4/CD107a+CD154-IFNg-IL2-TNFa+	IFNg- / IL2- / TNFa+ / CD154-
	CD4/CD107a-CD154-IFNg-IL2-TNFa+	

T Cell	Cytokines (%)	Cytokine combination naming
	CD4/CD107a+CD154+IFNg-IL2-TNFa- CD4/CD107a-CD154+IFNg-IL2-TNFa-	IFNg- / IL2- / TNFa- / CD154+
CD8+	CD8/CD107a+CD154+IFNg+IL2+TNFa+ CD8/CD107a+CD154-IFNg+IL2+TNFa+	IFNg+ / IL2+ / TNFa+ / CD107+
	CD8/CD107a-CD154+IFNg+IL2+TNFa+ CD8/CD107a-CD154-IFNg+IL2+TNFa+	IFNg+ / IL2+ / TNFa+ / CD107-
	CD8/CD107a+CD154+IFNg+IL2+TNFa- CD8/CD107a+CD154-IFNg+IL2+TNFa-	IFNg+ / IL2+ / TNFa- / CD107+
	CD8/CD107a-CD154+IFNg+IL2+TNFa- CD8/CD107a-CD154-IFNg+IL2+TNFa-	IFNg+ / IL2+ / TNFa- / CD107-
	CD8/CD107a+CD154+IFNg+IL2-TNFa+ CD8/CD107a+CD154-IFNg+IL2-TNFa+	IFNg+ / IL2- / TNFa+ / CD107+
	CD8/CD107a-CD154+IFNg+IL2-TNFa+ CD8/CD107a-CD154-IFNg+IL2-TNFa+	IFNg+ / IL2- / TNFa+ / CD107-
	CD8/CD107a+CD154+IFNg+IL2-TNFa- CD8/CD107a+CD154-IFNg+IL2-TNFa-	IFNg+ / IL2- / TNFa- / CD107+
	CD8/CD107a-CD154+IFNg+IL2-TNFa- CD8/CD107a-CD154-IFNg+IL2-TNFa-	IFNg+ / IL2- / TNFa- / CD107-
	CD8/CD107a+CD154+IFNg-IL2+TNFa+ CD8/CD107a+CD154-IFNg-IL2+TNFa+	IFNg- / IL2+ / TNFa+ / CD107+
	CD8/CD107a-CD154+IFNg-IL2+TNFa+ CD8/CD107a-CD154-IFNg-IL2+TNFa+	IFNg- / IL2+ / TNFa+ / CD107-
	CD8/CD107a+CD154+IFNg-IL2-TNFa- CD8/CD107a+CD154-IFNg-IL2-TNFa-	IFNg- / IL2+ / TNFa- / CD107+
	CD8/CD107a-CD154+IFNg-IL2-TNFa- CD8/CD107a-CD154-IFNg-IL2-TNFa-	IFNg- / IL2+ / TNFa- / CD107-
	CD8/CD107a+CD154+IFNg-IL2-TNFa+ CD8/CD107a+CD154-IFNg-IL2-TNFa+	IFNg- / IL2- / TNFa+ / CD107+
	CD8/CD107a-CD154+IFNg-IL2-TNFa+ CD8/CD107a-CD154-IFNg-IL2-TNFa+	IFNg- / IL2- / TNFa+ / CD107-

T Cell	Cytokines (%)	Cytokine combination naming
	CD8/CD107a-CD154+IFNg-IL2-TNFa+	IFNg- / IL2- / TNFa+ / CD107-
	CD8/CD107a-CD154-IFNg-IL2-TNFa+	
	CD8/CD107a+CD154+IFNg-IL2-TNFa-	IFNg- / IL2- / TNFa- / CD107+
	CD8/CD107a+CD154-IFNg-IL2-TNFa-	

Overall cytokine percentage expression (%) for each T cell (CD4+, CD8+) by stimulation antigen will then be calculated as:

- For CD4+: the sum of every CD4+ cytokine combination (%) where at least one of the 4 cytokines of interest (i.e., CD154, IFNg, TNFa, and IL-2) is positive [+] (regardless of CD107a positivity). That is, every CD4+ parameter combination except for the two below where expression is negative for all 4 cytokines of interest for CD4+:
 - CD4/CD107a+CD154-IFNg-TNFa-IL-2-
 - CD4/CD107a-CD154-IFNg-TNFa-IL-2-
- For CD8+: the sum of every CD8+ cytokine combination (%) where at least one of the 4 cytokines of interest (i.e., CD107, IFNg, TNFa, and IL-2) is positive (regardless of CD154 positivity). That is, every CD8+ parameter combination except for the two below where expression is negative for the 4 cytokines of interest for CD8+:
 - CD8/CD107a-CD154+IFNg-TNFa-IL-2-
 - CD8/CD107a-CD154-IFNg-TNFa-IL-2-

Missing values will not be imputed for this analysis.

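### SAP Table 1 lists IL2- gates for two of the 15 CD8+ categories labelled IL2+, so plots programmed from the gate column would show two wrong categories

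*SAP*

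**What the plan says.** SAP Section 2.6.1 derives each intracellular cytokine staining percentage in three steps. Positive cells are divided by the total CD4+ or CD8+ count, the same percentage for the DMSO background is computed and subtracted, and the result is set to 0 if the background is larger. For each T cell, "15 cytokine combinations (Table 1) per stimulation antigen will be calculated for summarization using the approach documented above".

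The worked example there adds the counts of the two gates that make up one combination: "461 (i.e., the CD4+ cells that also express CD107" marker, and the 6316 that do not. A gate here means one signed combination of CD107a, CD154, IFNg, IL2 and TNFa.

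Table 1 sets a pair of gates beside a label in every row. The first CD8+ row pairs "CD8/CD107a+CD154+IFNg+IL2+TNFa+ CD8/CD107a+CD154-IFNg+IL2+TNFa" with "IFNg+ / IL2+ / TNFa+ / CD107"; both quotes stop before a final plus sign. In that row gates and label agree.

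On cells negative for every cytokine the SAP says: "Note that the all-negative response categorization, where no cytokine is expressed, does not need to be calculated". The overall CD8+ response is defined separately, as the sum of "every CD8+ parameter combination except for the two below where expression is negative for the 4 cytokines of interest for CD8", and the two excluded gates are named.

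Section 6.6.4.1 shows the 15 combinations in polyfunctional profile plots for each T cell and antigen at two days, with the plus and minus signs printed under the plot.

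**The concern.** Two CD8+ rows contradict themselves. Their labels say IL2 positive and their gates say IL2 negative. The gate column looks operational rather than decorative, because the SAP calculates the Table 1 combinations by its documented approach and its example adds gate counts. The gate strings also resemble the data column names shown in that example, so copying them into code is a natural thing to do.

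If that happens, two bars in every CD8+ plot carry correct-looking signs over the wrong cell populations. One shows the CD107-only response a second time. The other shows the background-subtracted share of cells with no response at all, which will usually appear as an empty bar and so look plausible.

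The cross-references do little to protect against this. Section 2.6.1 twice sends the reader to Table 2 for the cytokine combinations, but Table 2 is the cohort table in Section 3.1.1. The reference beside the 15 combinations in Section 6.6.4.1 does not resolve.

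**Working it through.** **Inputs.** All come from SAP Section 2.6.1: the 15 CD4+ and 15 CD8+ rows of Table 1, the three-step calculation, the worked example and the definition of the overall CD8+ response. The plotted days come from Section 6.6.4.1. The CD107-negative row of the pair labelled "IFNg- / IL2- / TNFa+ / CD107" is printed on both sides of a page break with the same gates and is counted once.

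**1. The SAP's own example.** 461 + 6316 = 6777, and 6777/103111 = 6.573%. For DMSO, 3 + 16 = 19, and 19/101599 = 0.019%. The difference is 6.573 - 0.019 = 6.554%, as the SAP states. The calculation route is therefore clear: add the two gates of a combination, then subtract background.

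**2. Gates against labels.** Each printed gate was compared with its label. In the CD4+ block all 15 rows agree. In the CD8+ block 13 agree and two do not. The third row below is consistent and is shown for comparison.

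| CD8+ label | Gates printed (CD154+ and CD154-) | Gates the label implies |
|---|---|---|
| IFNg- IL2+ TNFa- CD107+ | CD107a+ IFNg- **IL2-** TNFa- | CD107a+ IFNg- IL2+ TNFa- |
| IFNg- IL2+ TNFa- CD107- | CD107a- IFNg- **IL2-** TNFa- | CD107a- IFNg- IL2+ TNFa- |
| IFNg- IL2- TNFa- CD107+ | CD107a+ IFNg- IL2- TNFa- | the same |

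The first row prints the same gates as the third. The gates in the second row are the two all-negative gates.

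**3. Coverage.** Five markers give 2^5 = 32 gates. Leaving out the two all-negative ones, 30 are needed.
- CD4+: 30 distinct gates printed, 30 of 30 covered.
- CD8+: 30 printed, 28 distinct (two appear twice). Two of the 28 are all-negative, so 28 - 2 = 26 needed gates are covered and 30 - 26 = 4 are missing. The missing four are CD107a+/- by CD154+/- with IFNg- IL2+ TNFa-.
- With IL2+ in the four gate names, the CD8+ block uses all 30 needed gates once each.

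**4. What the gate column would produce.** Let P be the percentage of CD8+ cells positive for at least one of the four cytokines.
- The category labelled IL2+ CD107+ equals the CD107-only value.
- The category labelled IL2+ only becomes (100 - P_stim) - (100 - P_DMSO) = P_DMSO - P_stim. With the floor applied to each combination it is max(0, P_DMSO - P_stim), which is 0 whenever stimulation raises total positivity, whatever the true IL2+ value.

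The documents give no CD8+ values, so the following figures for the IL2+ only category are assumptions.

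| Assumed P_DMSO | P_stim 0.10 points higher | P_stim 0.02 points lower | P_stim half of P_DMSO |
|---|---|---|---|
| 0.05% | 0 | 0.02% | 0.025% |
| 0.20% | 0 | 0.02% | 0.10% |
| 0.50% | 0 | 0.02% | 0.25% |

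A second illustration uses assumed counts per 100,000 CD8+ cells, antigen against DMSO: IL2 only 60 and 20, IL2 with CD107 10 and 2, CD107 only 300 and 200, other positive 130 and 30.
- IL2 only should be 0.060 - 0.020 = 0.040%. The totals are 500 and 252, so the gate column gives 0.252 - 0.500 = -0.248%, floored to 0.
- IL2 with CD107 should be 0.010 - 0.002 = 0.008%. The gate column gives 0.300 - 0.200 = 0.100%.

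**5. Reach.** 2 categories x 4 antigens x 2 days = 16 values, out of 15 x 4 x 2 = 120 for CD8+ (13.3%), or out of 240 for CD4+ and CD8+ together (6.7%), per group shown.

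**The case against.** The strongest objection is that the text was read from PDF by a program, and the mismatched rows lie in a segment where the layout changes (two gates per line) and one row is repeated. A shifted row or column cannot remove four gates from the table, but misread signs in near-identical strings remain possible. Against that, all four discrepancies are the same sign on the same marker, which fits a drafting slip, and the segment holds most of the CD8+ rows, so its location says little. The source page should be checked first.

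Second, the SAP points to the right answer elsewhere. The 15 labels are distinct and correct, the CD4+ block shows the pattern, and the all-negative gates are named and excluded from the overall response. A careful programmer would probably notice two identical bars and four unused data columns. This stands, and it is why the error is conditional on following the gate column.

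Third, the floor at 0 is written for total positive expression, and the worked example never uses it. Extending it to each combination is the natural reading of the documented approach, but it is a reading. Without the floor the IL2+ only bar would be negative whenever stimulation raises the total, which would be noticed.

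Fourth, the output is exploratory and descriptive, no test uses these categories, and 13.3% counts affected values rather than the size of the error. All of this is correct. It limits the importance of the point without removing the contradiction.

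**Conclusion.** The concern holds. Two of the 15 CD8+ rows in Table 1 list gates that contradict their labels, four needed gates are missing, and the all-negative gates are used where the SAP says they need not be. If the plots are programmed from the gate column, 16 of 120 CD8+ values per group shown are wrong; if from the labels, none are.

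This rests on the signs being as printed in the text read from PDF. The statement that the IL2+ only bar shows 0 also rests on applying the floor to each combination.

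The overall CD8+ response is correct under its own definition. It would go wrong only if someone summed the Table 1 rows as printed, which would count CD107-only twice, omit the IL2-only gates and include the all-negative ones. No safety, PSA or regimen-selection result is affected. Immunogenicity is, however, the one exploratory objective kept in the Phase 1 SAP, and these plots are the planned output for the 15 combinations, so the table should be corrected before programming.

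**What to change.** Check the source page of Table 1 first. If the signs are as read, change IL2- to IL2+ in four gate names of the CD8+ block:

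- Row IFNg-/IL2+/TNFa-/CD107+: `CD8/CD107a+CD154+IFNg-IL2+TNFa-` and `CD8/CD107a+CD154-IFNg-IL2+TNFa-`.
- Row IFNg-/IL2+/TNFa-/CD107-: `CD8/CD107a-CD154+IFNg-IL2+TNFa-` and `CD8/CD107a-CD154-IFNg-IL2+TNFa-`.

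In Section 2.6.1, point both references to Table 2 at the corrected Table 1. Add a programming check that the 15 CD8+ rows use 30 distinct gates and neither all-negative gate.

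The cost is four gate names, two table references and one check. No new data are needed.

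### SAP 2.6.1 gives two conflicting orders of operation for overall ICS expression, and the more natural one (floor each of 15 combinations, then sum) is biased upward near the noise floor

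*SAP*

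**What the plan says.** All of the definition is in SAP Section 2.6.1.

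- **Endpoint class.** The endpoint is the background-subtracted percentage of CD4+ or CD8+ cells "that positively express at least one of four cytokines".
- **Steps 1 to 3.** Step 1 takes the percentage of cells "with total positive cytokine expression (i.e. all combinations in Table 2"). Step 2 does the same for DMSO. Step 3 subtracts and, if background exceeds the antigen value, says "the percentage with positive expression for the stimulation antigen should be set to 0". Table 2 is the cohort table in Section 3.1.1; the combinations are in Table 1.
- **Worked example.** One combination (all four CD4+ cytokines, antigen 5T4) is taken through the three steps: "6.573 - 0.019 = 6.554"%.
- **Combinations.** For each T cell, "15 cytokine combinations (Table 1) per stimulation antigen will be calculated for summarization using the approach documented above".
- **Overall value.** This is *then* calculated, for CD4+, as "the sum of every CD4+ cytokine combination (%) where at least one of the 4 cytokines of interest" is positive, glossed as "every CD4+ parameter combination except for the two below". A parallel rule covers CD8+.

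Section 6.6.4.1 uses the overall value for descriptive summaries (absolute value, change and fold change from baseline), dot plots and stacked bars of medians. Fold change adds a small constant λ only when the Day 1 value is 0.

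**The concern.** The documented approach includes the floor in step 3. If it is applied to each of 15 combinations and the results are summed, a combination in which the stimulated well happens to exceed DMSO contributes its excess, while one that falls short contributes nothing. The shortfalls can no longer offset the excesses, so the sum is pushed upward by noise alone. The push grows with background, so it can differ between participants and visits.

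Steps 1 to 3, taken at their word, floor only the total. The SAP does not choose between the two, so two competent programmers could produce different ICS tables from the same data. The choice also decides how often the Day 1 value is exactly 0, and therefore which fold-change formula applies.

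**Working it through.** **1. The SAP's own figure.** (461 + 6316)/103111 × 100 = 6.573%. (3 + 16)/101599 × 100 = 0.019%. The difference is 6.554%, as stated. This is a single combination with a strong signal, so the floor never acts and the example cannot show which order is meant.

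**2. Where the floor would act in the same hypothetical data** (same combination, DMSO 0.0187%):

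| Antigen | Stimulated | Difference | After floor |
|---|---|---|---|
| PSA | 5/103404 = 0.0048% | −0.0139 | 0 |
| PAP | 1/103093 = 0.0010% | −0.0177 | 0 |
| STEAP1 | 0/106261 = 0% | −0.0187 | 0 |

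Flooring only the total would let these deficits offset excesses in the other 14 combinations. Flooring each combination discards them.

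**3. Direction.** Write d_k for the background-subtracted percentage in combination k. Then Σ max(d_k, 0) ≥ max(Σ d_k, 0) always. This needs no assumption about background.

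**4. Size with no true response.** The SAP gives no total background, so these inputs are assumptions: 100,000 cells per well, independent Poisson counts, the same rate in the stimulated and DMSO wells, and total background of 20 or 100 positive cells per 100,000 (0.02% or 0.10%).

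For an expected count μ in each well, the difference has standard deviation √(2μ), and its floored mean is about 0.399 × √(2μ). At 0.10% background split equally, μ = 100/15 = 6.67:

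- floor each, then sum: 15 × 0.399 × √13.33 = 21.9 cells, about 0.022%
- floor once on the total: 0.399 × √200 = 5.6 cells, about 0.0056%

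Simulation with 200,000 samples agrees. Within each range, equal shares give the top figure and the most uneven split tried (geometric) gives the bottom one.

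| Total background | Floor each, then sum: mean | Floor once: mean |
|---|---|---|
| 0.02% | 0.0061–0.0093% | 0.0025% |
| 0.10% | 0.0148–0.0217% | 0.0056% |

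The ratio runs from 0.0061/0.0025 = 2.4 to 0.0217/0.0056 = 3.9. At 0.10%, floor-each is above zero in over 99% of samples and floor-once in about 49%. Only the unfloored total averages zero.

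A separate run used the example's cell counts (103111 and 101599) and background of 1 to 50 per 100,000 in every combination. It gave means of 0.0078–0.0591% against 0.0022–0.0153%, and medians of 0.008–0.058% against 0.

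**5. Change from baseline.** With equal background at both visits and no true response, the simulated mean change is about 0 under either order. If background moves from 0.02% to 0.10%, the false mean change is 0.0148 − 0.0061 = 0.009% to 0.0217 − 0.0093 = 0.012% under floor-each, against 0.0056 − 0.0025 = 0.003% under floor-once.

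**6. With a true response of 0.050% and 0.10% background.** Floor-each reads 0.054–0.057% if the true cells are spread in proportion to background, and 0.061–0.067% if they sit in three combinations. Floor-once reads 0.050%. At a true response of 0.5%, spread in proportion to background, both read 0.500%.

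**7. Fold change.** Floor-once leaves about half of null baselines exactly 0, which triggers λ. Taking λ as half of one cell per 100,000 (0.0005%), a 0.050% response over a zero baseline gives (0.050 + 0.0005)/0.0005 − 1 = 100. In simulation, with a true response of 0.050% and backgrounds of 0.02% to 0.10%, the median fold change was roughly 50 to 70 under floor-once and 2 to 9 under floor-each. The first is largely produced by λ; the second is compressed by an inflated baseline.

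**The case against.** A reader might infer that the SAP defines overall ICS expression as a sum of floored values and so turns noise into T-cell responses. The documents do not support that.

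- **The definition is not settled.** Steps 1 to 3 operate on the total. The sentence defining the sum mentions neither subtraction nor flooring, and its gloss names raw columns split by CD107a status, so it could mean summing before subtraction. Section 6.6.4.1 also presents DMSO expression in the same way as the overall response, which implies that an unsubtracted total is computed too.
- **No participant is classed as an ICS responder.** Only ELISpot has a positivity threshold (Section 2.6.2) and a responder summary (Section 6.6.4.2). Above zero means only a percentage greater than 0.
- **ICS is not named as the main immunogenicity variable.** Flow cytometry and ELISpot share one exploratory endpoint, and ELISpot carries the only immunogenicity test. Protocol Section 4.1.1 bases regimen selection on safety data, and no sample size or alpha depends on ICS.
- **Flooring once is not a complete cure.** It keeps a smaller upward bias and makes fold change unstable.

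All four points stand and limit the finding. They do not remove it: the worked example runs the steps on a single combination, the text applies that approach to all 15, and the sum of percentages comes *then*. That makes floor-each the more natural reading, and nothing in the SAP rules it out.

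**Conclusion.** The SAP contains an unresolved contradiction about how overall ICS expression is computed. The direction of the difference between the two orders is certain. Its size rests on assumed backgrounds, equal rates in the paired wells and independent counts: for total backgrounds of 0.02% to 0.10% and no true response, about 0.006–0.022% under floor-each against 0.0025–0.006% under floor-once. This is material for responses near the noise floor, in absolute values and fold change, and negligible for strong responses. Mean change from baseline is unaffected when background is equal and there is no true response, but not when background shifts between visits. Because the endpoint is exploratory and descriptive, this is a correction that should be made before programming. It does not threaten the trial's conclusions on safety or PSA.

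**What to change.** In SAP Section 2.6.1:

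1. State that overall expression is the summed count of cells positive for at least one of the four cytokines, divided by the CD4+ or CD8+ count, minus the DMSO percentage for the same total, subtracted once.
2. State that floored combinations are never summed, and that the 15 combinations serve the polyfunctional profile plots only.
3. Leave the total unfloored for absolute values and change from baseline. Otherwise floor it once at the end and acknowledge the smaller upward bias that remains.
4. Correct the Table 2 references for the cytokine combinations to Table 1. Add a short worked example of an overall value in which some combinations fall below background.

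In Section 6.6.4.1, base the ICS interpretation on change from baseline, or apply the same λ to every participant when calculating fold change. The first is safer. A common λ stops the formula switching between participants, but it leaves the value of 100 for a zero baseline in step 7 of the working unchanged. If the total is left unfloored, say how fold change treats a zero or negative baseline.

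The cost is a few sentences and a few lines of code, with no new data.
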